Unanticipated serious adverse device effect (USADE).

- ISO14155/MEDDEV2.7.3 definition: Serious adverse device effect which by its nature, incidence, severity or outcome has not been identified in the current version of the risk analysis report
 - Note: The 'risk analysis report' refers to the most current risk documents for a given investigational device. The essence of the risk documents is captured under the Risk Assessment section of the device IB or the device section of a combination product IB.
- US FDA definition (Unanticipated adverse device effect (UADE)): Any serious adverse effect on health or safety, any life-threatening problem or death caused by, or associated with a device, if that effect, problem, or death was not previously identified in nature, severity, or degree of incidence in the application; or any other unanticipated serious problem associated with a device that relates to the rights, safety, or welfare of subjects.

^cProduct Complaint is: Any written, electronic or oral communication that alleges deficiencies related to the identity, quality, durability, reliability, safety, effectiveness, or performance of a drug, combination product, or device after it is released for distribution to market or clinic by either: (1) Amgen or (2) distributors or partners for whom Amgen manufactures the material. This includes all components distributed with the drug, such as packaging, drug containers, delivery system, labelling, and inserts. Examples include:

- Device that is damaged or broken
- · Bent or blunt needles
- Missing or illegible labeling
- Inability of customer to administer the product
- Product with an unexpected color, appearance, or particles
- Use error (i.e., an act or omission of an act that results in a different combination product or medical device response than intended by the manufacturer or expected by the user, where the user attempted to use the combination product or medical device in good faith and experienced difficulty or deficiency administering the product).

Reports of misuse of a combination product or medical device (i.e., the intentional and improper use of a combination product or medical device not in accordance with the authorized product information) are not considered Product Complaints.

Table 6. Aggregate reports^a (For all study types, as applicable):

Timeframe for submission to	Send to
Amgen	
Once per year and at the end of	NASCR
the study	Manager
Annually	NASCR
•	Manager
At the time of Sponsor submission	NASCR
to anybody governing research	Manager
conduct (e.g. RA, IRB etc.)	
At the time of Sponsor submission	NASCR
to anybody governing research	Manager
conduct (e.g. RA, IRB etc.) but no	
later than 1 calendar year of study	
completion	
	Amgen Once per year and at the end of the study Annually At the time of Sponsor submission to anybody governing research conduct (e.g. RA, IRB etc.) At the time of Sponsor submission to anybody governing research conduct (e.g. RA, IRB etc.) but no later than 1 calendar year of study

^a Specific requirements are to be outlined in the Research Agreement.

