1. PROTOCOL SUMMARY

a. Sponsor

Sponsor

Fundación Pública Andaluza para la Gestión de la Investigación en Salud de Sevilla (FISEVI)

Hospital Universitario Virgen del Rocío

[name]

[name]

[name]

[contact]

Coordinating Investigator

[name] Hospital Universitario Virgen del Rocío Haematology Department [name] [name]

[contact]

e-mail: [contact]

Steering Committee

[name], Spain [name], United Kingdom [name], Italy The list of local principal investigators will be included

Medical Monitor

[name] Hospital Universitario Virgen del Rocío [name] [name] [name]

[contact]

b. Study Title

A multicentre, randomized, open-label study of romiplostim plus dexamethasone vs dexamethasone in patients with newly diagnosed primary immune thrombocytopenia.

c. Protocol code

RODEX

d. Ethics Committee

The opinion of the Ethics Committee will be obtained in accordance with local legislation in each participating country.

e. Investigational product

Romiplostim and dexamethasone

f. Phase

Phase III

g. Study objectives

Primary objective:

To evaluate the superiority of romiplostim plus dexamethasone vs dexamethasone alone after 6 months (≥180 days) from treatment cessation in patients with newly diagnosed primary immune thrombocytopenia (ITP) in terms of sustained response off any ITP treatment (6mSROT-50) and without WHO grade 2 or more bleeding.

Maximum time on treatment with romiplostim will be 12 months (365 days). Then, patients will be followed up for 6 additional months (180 days) after stopping romiplostim.

Secondary objectives:

- To evaluate the superiority of romiplostim plus dexamethasone vs dexamethasone alone after 6 months (≥180 days) from treatment cessation in patients with newly diagnosed primary immune thrombocytopenia in terms of sustained response off any ITP treatment (6mSROT-30) and without WHO grade 2 or more bleeding.
- To evaluate the superiority of romiplostim plus dexamethasone vs dexamethasone alone after 12 months (≥365 days) from treatment cessation, if data available, in patients with newly diagnosed primary immune thrombocytopenia in terms of sustained response off any ITP treatment (12mSROT-30 and 12mSROT-50) and without WHO grade 2 or more bleeding.

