According to the International Working Group assessment [1] patients will be screened for study participation. Subjects who meet eligibility criteria will be enrolled. Once eligibility is confirmed, patient will be randomized. Randomization will be stratified by center with a 1:1 allocation using random block sizes, to receive dexamethasone 40 mg daily x 4 days only in the first cycle and subcutaneous romiplostim weekly for up to 12 months (ROM + DEX arm) or dexamethasone 40 mg daily x 4 days for up to 3 cycles every 14 to 28 days (DEX arm).

The monitoring will be the same in both arms with slight differences to allow for dose adjustments of romiplostim:

• In the ROM+DEX arm, patients will be reviewed weekly for 8 weeks (56 days). After Week 8, patients will be reviewed every 2 weeks (14 days) for

8 additional weeks and then monthly until Week 52 (365 days/12 months) from randomization.

- If romiplostim is modified, patients will be reviewed weekly until a stable dose of romiplostim is reached for at least 4 weeks (28 days).
 After that, patients will go on with visits every 2 weeks (14 days) for 8 weeks and then monthly until Week 52 (365 days/12 months) from randomization.
- In the DEX arm, patients will be reviewed weekly until the completion of dexamethasone cycles and for a minimum of 8 weeks (56 days). After that, every 2 weeks (14 days) for 8 additional weeks and then monthly until Week 52 (365 days/12 months) from randomization.

The following assessments will be done in these visits: platelets count, bleeding score, medication, HRU associated with the ITP or its treatment and loss of productivity

Quality of life will be evaluated at Day 1 (the day of administration of the first dose of study medication), Month 2 (week 8), Month 6 (Day 180), Month 12 (Day 365) and End of study Visit (visit 12 months after the last dose of study treatment). See Study schedule for more details.

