 - Definition of ER: proportion of patients with platelet count higher or equal than 30x10⁹/L and at least doble than baseline at first week (Day 7) from randomisation.
 - Definition of IR: proportion of patients with platelet count higher or equal than 30x10⁹/L in the first month (Day 30) from randomisation.
- To compare the difference of means between study arms of the maximum number of consecutive days with platelet response (CR, R, GR and TR) along the study period. We will evaluate them in the total sample and in the absence of any rescue treatment
- To compare the difference of means between study arms of the total number of days with platelet response (CR, R, GR and TR) along the study period. We will evaluate them in the total sample and in the absence of any rescue treatment.
- To evaluate and to compare the proportion of patients who need rescue treatments and proportion and time to treatment failures.
- To compare the time to loss of response (LoR) in patients who achieved response in both arms.
 - Definition of LoR: number of days from the first time the patient achieved a platelet count ≥30x10⁹/L until platelet count dropped below 30x10⁹/L measured on 2 occasions with more than 1 day apart or presence of bleeding
- To compare the difference between study arms in the proportion of patients requiring any rescue treatment along the study period.
- To compare the difference between study arms in the proportion of patients with adverse events (AEs), including serious adverse events (SAEs) and laboratory safety parameters. AEs will be graded according to National Cancer Institute Common Terminology Criteria for Adverse Events (CTCAE) version 5.0. Bleeding events will be carefully monitored.
- To compare the difference between study arms in the mean change in patients' bleeding from screening to Day 1, Week 8, Week 12, Moth 6, Moth 12andEnd of study Visit (visit 12 months after the last dose of study treatment) assessed with the ITP-bleeding tool in both arm.
- To compare the difference between study arms in the mean change in patients' quality of life from baseline Day 1 (the day of administration of the first dose of study medication) to Week 8, Month 6 (Day 180), Month12 (Day 365) from randomisation and End of study Visit (visit 12 months after

the last dose of study treatment) assessed with SF-36v2, FACIT-F and ITP-PAQ in both arms.

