Study time point	Days -28 to -1	Day 1	Weekly visits until Week 7	Week 8	Weekly or biweekly visits until Week 14 ¹¹	Week 16 and week 20	Week 24 (Month 6)	Monthly visits until Month 11	Month 12	Monthly visits until Month 17 ¹²	Month 18 ¹²	Unscheduled visit
			±1 days	±1 days	±1 days	±3 days	±7 days	±3 days	±7 days	±7 days	±7days	
Eligibility criteria	Х	Х										
Informed consent ¹	Х											
Medical history ³	Х											
Demographics ²	Х											
Pregnancy test ⁴	Х											
Randomization		Х										
Vital signs ⁵	Х	Х	Х	Х	X ⁵	Х	Χ	Х	Х	X	Х	X
Physical examination ⁶	Χ	Х	X ⁶	Х	X _e	Х	Х	Х	Х	Х	Х	X
Laboratory tests ⁷	Χ	Х	Х	Х	Х	Х	Х	Х	Х	X	Х	Х
WHO Bleeding score	Х	Χ	Х	Χ	Х	Х	Χ	Х	Х	X	X	X
HRU and loss of productivity8		Χ	X	Χ	X	Χ	Χ	X	Χ	X	Χ	
Quality of life questionnaires:9 SF36, FACIT, ITP PAQ		Χ		Χ			X		Χ		Χ	
ITP-BAT ¹⁰	Х	Χ		Χ	X ¹⁰		Χ		Х		X	
ITP medication		Χ	Х	Х	Х	Х	Χ	Х	X			
Rescue medication		Х	Х	Х	Х	Х	Х	Х	Х			Х
Concomitant medication		Χ	Х	Χ	X	Х	Χ	Х	X	X	Χ	X
AEs/Bleeding event reporting//splenectomy		Х	Х	Х	Х	Х	Х	Х	Х	Х	Х	Х

- 1. Informed consent must be signed and dated prior to any study-related procedure and before any data is recorded in the CRF.
- 2. Demographic data collection including sex, age, and ethnicity.
- 3. Medical history includes all information related to a new diagnosis of ITP and bleeding events history.
- 4. The pregnancy test at screening will be conducted 72 hours before first dose of study treatment.
- 5. Vital signs includes respiratory rate, body temperature, blood pressure, and pulse rate. They must be measured every week until week 8, then every 4 weeks.
- 6. Physical examination will be performed as per standard of care. Physical measurements include height (at screening) and weight (at screening, baseline and from then on every 4 weeks+/- 1 week). There shall be no dose adjustments until changes of 10% or more in weight.
- 7. Complete blood counts with differential, blood chemistry profiles (serum creatinine, ALT, AST, GGT, K, Na, LDH) and platelet counts.
- 8. HRU and loss of productivity shall be measured monthly.
- 9. Quality of life (SF36 v2, FACIT-F and IPT-PAQ) will be evaluated at Day 1, week 8, Month 12 and End of study Visit (visit 12 months after the last dose of study treatment).
- 10. ITP-BAT will be evaluated to screening, Day 1, Week 8, Week 12, Month 6, Month 12 and End of study Visit (visit 12 months after the last dose of study treatment).

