All information referring to adverse events must be recorded in the respective section of the CRF. AEs should be recorded according CTCAE v 5.0. All adverse events that occur during the period comprehended from the time of enrolment of the patient in the study (signing of the consent form) to 30 days after last dose of the investigational products will

be recorded. When one or more signs or symptoms correspond to a disease, the main diagnosis or syndrome will be notified. All adverse events will be followed until resolution or stabilization, or until it is determined that the study treatment or the patient's participation in the study has not been the cause. All adverse events still present at the end of the study period will be monitored until their final outcome is determined.

ii. Reporting of serious adverse events (SAEs)

All serious adverse events that occur during the clinical trial, whether or not they are related to the study drug, must be communicated immediately by e-mail or by fax within 24 h of receiving knowledge of the same or, at the latest, on the next working day at:

Unidad de Investigación Clínica y Ensayos Clínicos
Hospital Universitario Virgen del Rocío
Dpto. Farmacovigilancia
Email: [contact]
[name]
[name]
[contact]

[contact]

The investigator will collect information about the SAE on the respective form. At least these **four elements are mandatory** always to report any adverse event:

- Name or any identifier of a reporter
- **Subject** ID number
- At least one **suspect drug**: current dose, route, dates
- Adverse Event information:
 - Adverse Event Term Seriousness Criteria
 - o Adverse event outcome
 - Causality assessment

iii. Expectedness

IMP	RSI to be used for expectedness assessment	Relevant section to be used for expectedness assessment
Romiplostim	Amgen Romiplostim SPC Amgen Romiplostim IB	Section 4.8 Section 7.6
Dexamethasone	TAD Pharma Dexamethasone SPC	Section 4.8

iv. Reporting of serious adverse events (SAEs) to Health Authorities

The sponsor is responsible for notifying to the Health Authorities of all suspected serious adverse reactions and unexpected, which occurred in the clinical trial. This communication shall be made within the time limits established by current legislation.

v. Follow-up of AEs and SAEs

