- To compare the time to first response (R) in both arms, Kaplan-Meier method will be used. Patients who not achieve R will be censored at the date of the last followup. Median and 95% CI, number of events and censored and risk number of patients will be provided. Log rank test will be used to compare time to first response between treatment arms. We will evaluate this in the total sample and in the absence of any rescue treatment.
- The proportion of patients with ER at Day 7 and IR at Day 30 from randomisation will be calculated and corresponding 95% CIs for each study arm will be provided.
 A Chi- square test or Fisher test if applicable will be used to compare the proportion of each endpoint between treatment arms.
- Descriptive statistics (mean, median, standard deviation, min, max, Q1 and Q3) and Student's t test will be used to compare the duration of platelet response through the following endpoints:
 - maximum number of consecutive days with platelet response (CR, R, GR and TR) along the study period and,
 - total number of days with platelet response (CR, R, GR and TR) along the study period in both arms. We will evaluate them in the total sample and in the absence of any rescue treatment.
- To compare the time to loss of response (LoR) in the subgroup of patients who achieve R (rITT population) between both arms, Kaplan-Meier method will be used. Patients who do not achieve LoR will be censored at the date of the last follow-up. Median and 95% CI, number of events and censored and risk number of patients will be provided. Log rank test will be used to compare time to first response between treatment arms.

 The proportion of patients requiring any rescue treatment along the study period will be calculated and corresponding 95% CIs for each study arm will be provided.
 A Chi-square test or Fisher test if applicable, will be used to compare the proportion between treatment arms.

Frequency and proportion of patients with adverse events, including bleeding events measured by the WHO bleeding scale will be provided. A Chi-square test or Fisher test if applicable will be used to compare the proportion between treatment arms.

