Safety assessment will consist of monitoring adverse events (AEs), including serious adverse events (SAEs) and laboratory safety parameters. AEs will be graded according to National Cancer Institute Common Terminology Criteria for Adverse Events (CTCAE) version 5.0. Bleeding events will be carefully monitored. AE terms will be coded using MedDRA (lastest version). The description of number and percentage of patients with each adverse event ordered by SOC/PT by grade and total will be summarized descriptively by treatment group.

The number of patients experiencing AEs and number of AEs will be summarized by treatment group using frequency counts.

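### The two rules for recording adverse events conflict and neither gives the arms equal observation time, yet crude adverse-event proportions are tested between arms

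*Protocol*

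**What the plan says.** **Recording rule.** Section 10.c.i has all AEs recorded from "signing of the consent form) to 30 days after last dose of the investigational products".

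**Treatment length.** The Protocol Summary gives the DEX arm "dexamethasone 40 mg daily x 4 days for up to 3 cycles every 14 to 28 days". For the other arm it says: "Maximum time on treatment with romiplostim will be 12 months (365 days").

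**Schedule.** Table 3 has a row "AEs/Bleeding event reporting//splenectomy", ticked in both arms at every visit from baseline to the End of study Visit. That visit stands at Month 18 in the DEX table and Month 24 in the romiplostim table.

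**Other safety text.** Section 10.c.i also has the investigator ask about AEs at every visit. Section 10.c.ii makes serious adverse events (SAEs) reportable whenever they occur in the trial. The Bleeding Events paragraph of the study procedures has bleeding assessed at each visit and entered on the Event CRF. Section 8.c follows everyone for 12 months from randomisation and at least 6 months off treatment.

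**Analysis.** A listed secondary outcome is "To compare the difference between study arms in the proportion of patients with adverse events (AEs), including serious adverse events (SAEs"). Section 11.e.i states "Frequency and proportion of patients with adverse events, including bleeding events measured by the WHO bleeding scale will be provided" and compares the proportions by chi-square or Fisher test. Section 11.e.ii adds: "The number of patients experiencing AEs and number of AEs will be summarized by treatment group using frequency counts". No common time window or rate per patient-time is stated.

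**The concern.** The proportion of patients with at least one AE rises with the time over which AEs are recorded. If one arm is watched several times longer than the other, that proportion will be higher there even when the drugs are equally safe, and the planned test will tend to report a difference in safety that is really a difference in observation time. The direction is against ROM+DEX.

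There is also a problem of data capture. A site following section 10.c.i stops recording non-serious AEs in a DEX patient by Day 90 at the latest. A site following Table 3 continues to Month 18. Sites may therefore differ, and non-serious events never entered may not be recoverable at analysis. The comparison matters because section 9.b starts romiplostim above the labelled dose and promises close safety monitoring, and the benefit/risk text leans on reducing long-term steroid side effects.

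**Working it through.** **Inputs from the protocol.** Dosing schedules and maximum treatment time (Protocol Summary), the 30-day rule (10.c.i), End of study at Month 18 and Month 24 (Table 3), and 63 patients per arm (11.b). The protocol gives no AE rate and no window in days, so there is no AE figure of its own to reproduce. The 63 serves only as the arm size. It agrees with the stated assumptions to within one patient: 30% versus 56.6% at 80% power and two-sided 5% needs 54 per arm; 54 × 1.15 = 62.1, rounded up to 63, and 54 / 0.85 = 63.5, rounded up to 64.

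**Step 1: windows under 10.c.i, counted from Day 1.**
- DEX, one cycle: last dose Day 4, window ends 4 + 30 = Day 34.
- DEX, three cycles 14 days apart: last dose 1 + 28 + 3 = Day 32, window ends Day 62.
- DEX, three cycles 28 days apart: last dose 1 + 56 + 3 = Day 60, window ends Day 90.
- ROM+DEX, maximum: 365 + 30 = Day 395.
- ROM+DEX, shortest complete taper with immediate response: last dose about Day 106 to 127, depending on how the taper is read, so the window ends about Day 136 to 157. I use 143 days (last dose Day 113) for this case. Withdrawal or treatment failure can end it sooner.

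The maximum ROM+DEX window is 395 / 90 = 4.4 to 395 / 34 = 11.6 times the DEX window.

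**Step 2: windows under Table 3.** Month 18 versus Month 24, a ratio of 24 / 18 = 1.33.

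**Step 3: effect on the test.** Assume the same constant rate of first AEs in both arms, 0.05 or 0.10 per patient-month. These rates are assumptions. The proportion with an AE is P = 1 − exp(−rate × days / 30.4). For example, at 0.10 and 90 days, P = 1 − exp(−0.296) = 26%; at 395 days, P = 1 − exp(−1.299) = 73%. The chance that the two-sided 5% chi-square test (no continuity correction) rejects with 63 per arm is summed exactly over the two binomial distributions.

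| Windows, DEX vs ROM+DEX | P at 0.05/month | Rejects | P at 0.10/month | Rejects |
|---|---|---|---|---|
| 90 vs 143 days | 14% vs 21% | 18% | 26% vs 38% | 30% |
| 90 vs 250 days (assumed intermediate course) | 14% vs 34% | 76% | 26% vs 56% | 95% |
| 90 vs 395 days | 14% vs 48% | 99% | 26% vs 73% | about 100% |
| 18 vs 24 months (Table 3) | 59% vs 70% | 24% | 83% vs 91% | 23% |
| 365 vs 365 days (common window) | 45% vs 45% | 6% | 70% vs 70% | 5% |

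With no true difference, rejection should be near 5%. Only the common window gives that.

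**The case against.** The case against has real weight.

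- **The 30-day limit is not the only rule.** Table 3, the enquiry at every visit and the follow-up in section 8.c all carry safety recording further. A reader might infer that the protocol fixes a design of 1 to 3 months against 13 months. It does not: it states two incompatible windows. It is also arguable that the follow-up ticks in Table 3, whose row covers bleeding and splenectomy as well, do not extend general AE recording. The text does not settle this.
- **Bleeding and SAEs are not clearly cut off.** A reader might infer that bleeding after relapse in DEX is lost after Day 90. The documents do not support that: bleeding is assessed and reported at every visit, grade 2 or worse bleeding is part of the primary endpoint through 6 months off treatment, and SAEs are reportable throughout. What can be lost is non-serious, non-bleeding AEs.
- **Day 395 is a maximum.** Responders taper and stop, and some patients leave treatment early. Near-certain false significance is the top of the range and does not describe every case.
- **Secondary results are labelled exploratory, the safety section is descriptive, and exposure-adjusted rates are ordinary SAP content.** This lowers the stakes, and the absence of rates is not in itself a fault. But the label addresses the number of tests and does not remove a bias built into one of them. Nor can a SAP restore events that sites were told not to record.

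**Conclusion.** The point stands in limited form. Section 10.c.i and Table 3 contradict each other on how long AEs are recorded, and for a full romiplostim course neither gives the arms equal windows. The crude chi-square or Fisher comparison that the protocol itself fixes is therefore biased against ROM+DEX. With truly equal rates, the chance of a significant difference runs from about 18% to nearly 100% under 10.c.i, depending on how long romiplostim is given, and is about 23-24% under Table 3.

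These figures rest on assumed constant rates of 0.05 to 0.10 per patient-month and on every patient in an arm having the same window. Actual windows will vary between patients, so the figures show a range and do not predict a result. The primary efficacy test is unaffected. This should be fixed, but it does not make the safety data as a whole unreadable.

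**What to change.** 1. Reconcile section 10.c.i with Table 3 so that AEs are recorded in both arms at least to Day 365 from randomisation.
2. In section 11.e.i, make the between-arm comparison of AE proportions over the common Day 1-365 window. Recording to End of study alone would not equalise the arms, because that visit is Month 18 in one and Month 24 in the other.
3. Add event rates per patient-year over all follow-up.
4. Show on-treatment AEs (to last dose plus 30 days) by arm, descriptively and without a test.

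The cost is a short amendment to sections 10.c.i and 11.e, and some additional recording of late non-serious AEs in DEX. The visits and the AE row already exist, and section 8.c already follows all patients for 12 months. The change is best made early, since unrecorded non-serious events may not be recoverable.
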